8.7 Safety Endpoints

Safety analysis will be performed on the Safety Analysis Set.

8.7.1 Adverse events

A treatment-emergent adverse event (TEAE) is defined as an event that first occurred or worsened in severity after the first administration of study drug (Visit 3) but on or prior to the end of study. Adverse events will be mapped to system organ class (SOC) and preferred term using MedDRA, version 17.1 or later.

The number and percent of subjects who had TEAEs, serious TEAEs, AEs with death outcome, AEs that led to study drug withdrawal, and AE of interest will be summarized. AE of interest is AEs which may indicate potential abuse. The list of abuse related AE of interest is in [Appendix 2](#) to [Appendix 4](#). For withdrawal symptoms (Error! Reference source not found.), only the preferred terms occurred after last dose of treatment will be considered as withdrawal. Adverse events will also be summarized by SOC and preferred term and presented by maximum reported intensity and by Investigator's causality assessment. Corresponding data listings will be presented as well.

An AE that was present at treatment initiation, but resolved and then reappeared while the subject was on treatment, is a TEAE (regardless of the intensity of the AE when the treatment was initiated). If the start date of an AE is incomplete and cannot be categorized as occurring before or after the first dose, then the AE will be considered as TEAE. If the start time of AE is provided then the AE start date and time will be used to classify the AE as TEAE or not. If the

start time is not provided and the AE occurs on the same day of first study drug administration then the AE will be classified as TEAE.

The duration of AEs will be calculated, partial dates for AE start, will be imputed as follows: If AE start date is missing, the missing day will be imputed as the first day of the month if the month of AE occurrence is after the month of first dose date. If the month of AE occurrence is the same month as first dose then the missing day will be imputed as the same day as the first dose date. If the month of AE occurrence is not the same as the month of first dose date then the missing day will be imputed as the first day of the month. If AE start month is missing and AE start year is the same as the year of the first dose, the missing month will be imputed as the month of the first dose date. If AE start year is not the same as the first dose year, the missing month and day of AE occurrence will be imputed as January 1 of the year. If AE start year is missing, no imputation will be done. If there is insufficient data for AE start date to make this comparison, the AE will be considered as treatment-emergent.

Partial dates for AE stop date will be imputed as follows: if the day and month are both missing, the missing date will be imputed as the treatment termination date or 14 days after last dose of study drug whichever is later. If only the day is missing but month and year are present, the missing day will be imputed as the last day of the month. No imputation will be done if the year is missing. For unresolved/resolving/unknown AEs with a completely missing stop date, there will be no imputation.

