5.1.1 Rollover Subjects

Rollover Subjects must also meet the following criteria in order to be eligible for the study:

1. Must fully complete through the End of Treatment Visit of Study 14-181-07 or Study 14-181-12 prior to receiving study drug.

2. Have no break in treatment with study drug.

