6.0 TREATMENT PLAN

6.1 Screening Period (Visits 1-2)

Subjects will provide written informed consent to participate in the study before completing any protocol-specified procedures or evaluations. Subjects will be eligible to enter the Screening Period in 2 ways:

- If they are currently enrolled in and expected to complete Study 14-181-07 or Study 14-181-12 through the End of Treatment Visit.; these subjects (either on NKTR-181 or placebo) may be eligible to enroll in this study as a **Rollover Subject**
- If they have a clinical diagnosis of moderate to severe chronic low back pain for > 3 months, and are non-tolerant to opioid analgesics (i.e., currently taking no less than 10 mg but no more than 60 mg MSE/day for at least the 7 days prior to signing the ICF); such subjects may be eligible to enroll in this study as a **De Novo Subject**

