6.1.1 Rollover Subjects

Rollover Subjects should have no break in treatment with study drug. Visit 1 (Screening) will take place concurrently with a scheduled, on treatment clinic visit, during Study 14-181-07 and Study 14-181-12.

The End of Treatment Visit in Study 14-181-07 and Study 14-181-12, where the subject has completed tapering to the 100-mg NKTR-181 BID starting dose for this study, will be the first visit of the Treatment Period (Visit 3). There is no Visit 2 for Rollover Subjects.

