10.0 ASSESSMENT OF SAFETY

10.1 Adverse Events and Serious Adverse Events

10.1.1 Adverse Events Definition and Assessment

An AE is defined as any untoward medical occurrence in a subject who is administered a medicinal product and that does not necessarily have a causal relationship with this treatment.

An AE can therefore be any unfavorable and unintended sign, symptom, or disease temporally associated with the use of a medicinal product, regardless of whether or not it is considered related to the medicinal product. An AE can also arise from any use of the drug and from any route of administration, formulation, or dose. This definition includes intercurrent illnesses or injuries, and exacerbation of preexisting conditions as well as events attributed to protocol-mandated procedures. Clinical laboratory abnormalities will only be reported as AEs if they are deemed clinically significant by the Investigator and/or are associated with signs and symptoms, require treatment, or require follow-up.

An AE does not include the following:

- A medical or surgical procedure (e.g., surgery, endoscopy, tooth extraction, or transfusion); an AE is the underlying condition that leads to the procedure.
- Preexisting diseases or conditions present or detected before the start of study drug administration that do not worsen or increase in severity or frequency after the administration of study drug.
- Situations where an untoward medical occurrence has not occurred (e.g., hospitalization for elective surgery for a condition that has not worsened on study, social and/or convenience admissions to grant families a respite in caring for a subject).
- Adverse events that start in Study 14-181-07 and Study 14-181-12 and are ongoing during this study will continue to be followed for Rollover Subjects.

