10.6 Medical History

Relevant and significant medication history, including history of substance or opioid abuse, medical/surgical history, and concurrent illnesses will be collected for all subjects and noted as to whether the condition is active. All relevant medical history will be collected and carried forward for Rollover Subjects. Ongoing adverse events that occurred in Study 14-181-07 and Study 14-181-12 will continue to be followed for Rollover Subjects.

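### The TEAE definition restarts at Visit 3, so events that began on NKTR-181 in a feeder study and persist unchanged drop out of TEAE incidence and rates

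*SAP*

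**What the plan says.** **TEAE definition.** SAP 8.7.1 counts "an event that first occurred or worsened in severity after the first administration of study drug (Visit 3" of this study). It also counts recurrences: "An AE that was present at treatment initiation, but resolved and then reappeared while the subject was on treatment, is a TEAE". An event whose start date is too incomplete to place before or after first dose is treated as a TEAE. Nothing is said about subjects who were already taking NKTR-181.

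**Who the Rollovers are.** Protocol 6.1 admits subjects from both feeder arms: "these subjects (either on NKTR-181 or placebo) may be eligible". Protocol 5.1.1 requires that they "Have no break in treatment with study drug". Under Protocol 6.1.1, Visit 3 is the feeder study's End of Treatment Visit, "where the subject has completed tapering to the 100-mg NKTR-181 BID starting dose for this study".

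**Recording of ongoing feeder events.** In Protocol 10.1.1, under the lead-in "An AE does not include the following", the last bullet reads: "Adverse events that start in Study 14-181-07 and Study 14-181-12 and are ongoing during this study will continue to be followed for Rollover Subjects". Protocol 10.6 repeats, in the medical history section: "Ongoing adverse events that occurred in Study 14-181-07 and Study 14-181-12 will continue to be followed for Rollover Subjects". Footnote 5 to the Schedule of Assessments says the same. No section names the form on which these events are recorded or the table in which they appear.

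**Reporting.** Protocol 11.9.3 plans a TEAE rate per 100 patient-years. Protocol 11.1 and 11.9 present safety for De Novo, Rollover and all subjects combined.

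**The concern.** For a De Novo Subject, Visit 3 is the start of NKTR-181. For a Rollover from a feeder NKTR-181 arm it is a point part-way through continuous exposure. One anchor therefore treats the same experience in two ways. Constipation that starts in week 1 and persists for a year is a TEAE in the De Novo Subject. Constipation that started on NKTR-181 in the feeder study and persists at the same severity for the same year is not a TEAE in the Rollover. Both subjects are in the combined denominator and both contribute patient-years.

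The primary objective is long-term safety and tolerability. Effects that do not go away on continued treatment are central to that question, and they are the ones the definition removes. The error runs in one direction, towards lower TEAE figures. Showing Rollovers separately, or by feeder treatment as SAP 7.1 allows if necessary, does not put the missing events back.

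**Working it through.** The plan states no figure on this point, so there is none to reproduce. The check is a reading of the definitions followed by illustrative arithmetic.

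**Step 1: classify each possible course.** Take a feeder-NKTR-181 Rollover with an event that began on drug and was present at Visit 3.

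| Course after Visit 3 | TEAE under SAP 8.7.1? |
|---|---|
| Worsens in severity | Yes |
| Resolves, then reappears on treatment | Yes |
| Start date too incomplete to place | Yes |
| Continues, neither worse nor resolved | No |

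Only the last row is lost. It is lost from TEAE incidence, from serious TEAEs if serious, and from the rate in Protocol 11.9.3.

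**Step 2: is there another route into the tables?** SAP 8.7.1 also lists AEs with death outcome, AEs leading to study drug withdrawal, AEs of interest, and AEs by system organ class and preferred term, with listings. Protocol 11.9.3 tabulates AEs and AEs leading to discontinuation. None of these is worded as TEAE-only. They can show a persisting event only if it is held as an AE in this study's database, and three parts of the protocol leave that unsettled:

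- Protocol 10.1.1 puts feeder-onset events in the list of what is not an AE, in a sentence that says they are followed.
- Another bullet in that list excludes conditions present before study drug starts that do not worsen. If the start means Visit 3, it covers the same events.
- Protocol 10.1.2 sends events between consent and first dose to medical history unless a protocol procedure caused them. Rollovers have Visit 1 while still on feeder treatment (Protocol 6.1.1), so read literally an event arising on NKTR-181 between Visits 1 and 3 becomes medical history here.

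**Step 3: illustrative size.** From the documents: about 600 subjects (Protocol 11.2), about 250 De Novo (Protocol 5.1.2). Implied Rollovers = 600 − 250 = 350, or 58% of 600. Not in the documents, so assumed: the share f of Rollovers who took NKTR-181 in the feeder study, and the share q of those with an unchanged ongoing event.

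Affected subjects = 350 × f × q.

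- Low, f = 40%, q = 5%: 140 × 0.05 = 7 (2% of Rollovers, 1.2% of 600).
- High, f = 60%, q = 20%: 210 × 0.20 = 42 (12% of Rollovers, 7.0% of 600).

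**Step 4: effect on one preferred term.** Let q now be the carry-over share for that term and r the new-onset risk in those without it.

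- TEAE-only incidence = (1 − q) × r. With q = r = 10% (assumed): 0.90 × 0.10 = 9.0%.
- With carried-over events shown = q + (1 − q) × r = 0.10 + 0.09 = 19.0%.

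The gap within the group equals q, here 10 points. With f = 50% the group has 175 subjects, and the gap in the combined column is 175 × 0.10 / 600 = 2.9 points.

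**Step 5: effect on any-TEAE incidence.** A subject leaves this numerator only if they have no other TEAE in the study. Take 175 subjects and 10–30% with an ongoing event (17.5 to 52.5 subjects). The ceiling is 10–30 points in the group and 2.9–8.8 points of 600. If 40–80% have another TEAE, independently (assumed), the loss is 10% × 0.20 = 2 points to 30% × 0.60 = 18 points in the group. In the combined column it is 3.5/600 = 0.6 to 31.5/600 = 5.3 points.

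**The case against.** The strongest reply is that little is lost. Worsened, recurrent and undatable events count. Rollovers reach 100 mg BID by taper and may then be titrated upwards, so many feeder events may resolve and return, or worsen, and so qualify. A persisting event that makes a subject stop falls, as worded, in the AE-leading-to-withdrawal summary, the discontinuation reasons (SAP 8.1) and the time to discontinuation due to AE (SAP 8.6.3). Somnolence is also on the SAP's list of abuse-related AEs of interest. The feeder studies may report the events too, though that lies outside these documents.

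Much of this stands. A reader might infer that these events are excluded as AEs altogether and counted nowhere; the documents do not support that. The Protocol 10.1.1 bullet conflicts with its own lead-in, two other places say the events are followed, and several tables are not limited to TEAEs. The definition also takes no account of cause: it applies equally to ongoing events in feeder-placebo Rollovers.

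What does not stand is that the other tables settle the matter. They depend on a recording rule that the protocol leaves contradictory. The TEAE counts and rate omit unchanged events in any case. Feeder-study reporting cannot show whether an event resolved, persisted or led to stopping during this trial.

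A reader might also conclude that the anchor should simply move to the first feeder dose. That would bring in events that resolved before Visit 3. It would also set them against exposure that SAP 8.6.3 starts at this study's first titration dose, and it risks counting the same events twice if studies are pooled.

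**Conclusion.** The point holds for one defined class: events that began on NKTR-181 in a feeder study and continue past Visit 3 without worsening or resolving. For these, TEAE incidence, serious-TEAE counts and the TEAE rate are biased low in the feeder-NKTR-181 Rollovers and, by preferred term, in the combined column. Whether the other AE tables show them is unsettled, because Protocol 10.1.1 is contradictory.

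The size cannot be derived from the documents. The range of 7 to 42 affected subjects rests on an assumed 40–60% feeder-NKTR-181 share and 5–20% carry-over. A reader might take 10–30 points in the group and 3–9 points overall as the expected bias in any-TEAE incidence. Those are at most ceilings: both inputs are assumed, no affected subject may have another TEAE, and none of the ongoing events may later qualify as a TEAE.

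A reader might further infer that the combined column makes the drug look better tolerated than it is in new users. De Novo Subjects are reported separately, and selection of feeder-study completers is a different issue that the anchor neither causes nor cures. The defect does not invalidate the safety analysis, but it bears on the primary objective and is cheap to correct.

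**What to change.** 1. **Protocol 10.1.1, 10.1.2 and 10.6.** Move the feeder-onset bullet out of the list of what is not an AE. State that feeder events ongoing at Visit 3 are recorded in this study as AEs, with their feeder-study onset date and severity. Reconcile this with the preexisting-condition bullet, with the medical-history rule in 10.1.2 and with 10.6.
2. **SAP 8.7.1.** Keep the Visit 3 TEAE definition. For Rollovers who received NKTR-181 in the feeder study, add a table by preferred term of events that emerged on NKTR-181 there and were ongoing at Visit 3, with outcome in this study: resolved, persisting, or led to discontinuation.
3. **SAP 8.7.1.** State that the AE-leading-to-withdrawal and serious-event tables include these events.
4. **Optional summary.** Any TEAE summary anchored at the first feeder NKTR-181 dose should be supplementary and should use matching feeder person-time in the denominator.

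The cost is some wording and one or two tables, using events that sites must already follow. The grouping by feeder treatment is already in SAP 7.1. The downside is somewhat less favourable AE figures for Rollovers.

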Statistical Methods:	
Summaries for the assessment of long-term safety will be presented by De Novo and Rollover Subjects separately and for all subjects combined. The frequency and percentage of subjects experiencing treatment-emergent adverse events (TEAEs), serious adverse events (SAEs), and AEs leading to withdrawal from the study drug will be tabulated by Medical Dictionary for Regulatory Activities (MedDRA) system organ class, preferred term, severity, and relationship to the study drug. Laboratory test results, vital signs, ECGs, SOWS, COWS, and change from baseline will be summarized using descriptive statistics. The relationship between duration of exposure and the frequency and severity of AEs will be examined. Time-to-event endpoints will be estimated using the Kaplan-Meier method. Change over time from baseline in each question and metric of the mBPI-SF will be summarized using descriptive statistics.

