11.9.3 Adverse Events

Adverse events will be coded by system organ class (SOC) and preferred term using the Medical Dictionary for Regulatory Activities (MedDRA), version 17.1 or later. The incidence of treatment emergent adverse events (TEAEs) will be presented by severity and relationship to study drug as perceived by the Investigator.

Adverse events, serious adverse events (SAEs), AEs by intensity, AEs by causality, AEs leading to death, and AEs leading to study discontinuation will be tabulated by System Organ Class and Preferred Term.

The event rate (per 100 patient years) of TEAEs by preferred term will be calculated and summarized descriptively. The relationship between drug exposure and the frequency and severity of AEs will be examined.

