11.10.2 Time to Stabilization of Pain Scores During the Study

The time to stabilization of pain scores since the first dose during the study will be estimated using the Kaplan-Meier method.

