8.5 Study Drug Exposure and Drug Compliance

Duration of exposure to study drug, cumulative dose of the study drug, and compliance of the study drug will be summarized for NKTR-181 on the Safety Analysis Set for the overall study period based on the Safety Analysis Set. The exposure duration of the study drug will be also summarized by time interval (e.g., ≥ 1 month, ≥ 2 months, ..., ≥ 12 months, and > 13 months).

The exposure duration (days) will be calculated as the number of days exposed to study drug: date of last dose - the date of first dose + 1.

The cumulative dose (mg) will be calculated as the sum of the number of tablets taken times the dosage per tablets at each dosage level. A subject's compliance of the study drug will be calculated according to the following:

$$\text{Compliance} = \frac{\text{number of tablets taken}}{\text{number of tablets planned}} \times 100$$

Compliance will be calculated based on the drug administration recorded in the CRFs. The number of tablets taken will be calculated as the total number of tablets dispensed minus the total number of tablets returned. If the number of returned tablets is missing due to any reason, it will be assumed that the subject took all dispensed tablets during that period. For those subjects who are lost to follow-up, it will be assumed that they took the number of dispensed tablets up until the last day of contact.

The number of tablets planned will be calculated as the prescribed number of tablets per day multiplied by the number of days potentially exposed to the study drug:

$$n \times (\text{the date of last dose} - \text{the date of first dose} + 1)$$

where n is related to the dose level. n is 2 for 100mg and 200mg, n is 4 for 300mg and 400mg, and n is 6 for 500mg and 600mg. The number of tablets planned will be adjusted for the first dose and the last dose time of the study drug.

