8.7.4 MADDERS™

Abuse-related events, also called misuse- and abuse-related events, consists of a related group of phenomena that include actual abuse (i.e., use intended to produce a euphoric effect), misuse (use outside of prescribing instructions to produce a therapeutic effect), suicide-related events, therapeutic error, overdose, diversion, addiction, withdrawal, tampering, and diversion (Smith, 2013). Until recently, these terms were used inconsistently, and consensus definitions of these terms for the purpose of clinical trials were not available, making it impossible to reliably quantify the rate of these events in studies.

Investigators are trained to identify any potentially abuse-related event, and at the time of identifying the event complete a Supplemental Adverse Event Form. In addition, a Supplemental Drug Accountability Form is completed for any subjects who have drug accountability discrepancies identified at any visit. Each time either of these events is completed, a Classification Form is completed by the investigator indicating the investigator's classification of the event in question. Finally, all subjects complete an interview-based assessment at the final visit of the study to identify any undetected abuse-related events that may have occurred during the study. Any events that have led to the completion of a Classification Form are provided to an Adjudication Committee for review and final classification.

Incidence of aberrant drug behavior according to MADDERS™ assessment will be summarized. Incidence per person-month will be summarized if applicable.

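### The SAP omits the exposure-adjusted adverse-event analyses that the protocol commits to, with several other promised outputs, and its section on changes from protocol lists none of this

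*SAP*

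**What the plan says.** Protocol 11.9.3 makes two firm commitments on adverse events. The first is "The event rate (per 100 patient years) of TEAEs by preferred term will be calculated and summarized descriptively". The second is "The relationship between drug exposure and the frequency and severity of AEs will be examined"; the synopsis repeats it and makes clear that time on drug is meant: "The relationship between duration of exposure and the frequency and severity of AEs will be examined".

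SAP 8.7.1 plans to summarise "The number and percent of subjects who had TEAEs, serious TEAEs, AEs with death outcome, AEs that led to study drug withdrawal", together with AEs of interest. It then breaks AEs down by SOC, preferred term, maximum intensity and causality, and gives rules for partial dates. It contains no event rate, no patient-time denominator and no AE table by exposure, dose or time. A TEAE is one that starts or worsens "after the first administration of study drug (Visit 3) but on or prior to the end of study".

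Three other protocol outputs are affected:

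- Protocol 11.10.2: "The time to stabilization of pain scores since the first dose during the study will be estimated using the Kaplan-Meier method".
- Protocol 11.9.7 asks for individual items as well as totals of the COWS and SOWS. SAP 8.7.2 plans totals only.
- Protocol 11.9 presents all safety analyses for De Novo Subjects, Rollover Subjects and everyone combined. SAP 8.7.5 tabulates laboratory results by treatment arm. SAP 8.7.6 tabulates vital signs and ECGs by titrated dose level.

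SAP 9.0, the section for changes from the protocol, is marked as not applicable.

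**The concern.** Long-term safety is the primary objective, so AE frequency over time is the study's main output. A crude percentage of subjects with an event depends on two things: how often events occur and how long subjects stay on drug. Two groups with the same event rate but different retention will show different percentages. Unequal retention is plausible here: Rollover Subjects must have completed a feeder study (protocol 5.1.1), and De Novo Subjects have not been selected in that way.

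Protocol 11.1 leaves the detailed methodology to the SAP. With the SAP silent, nothing fixes in advance whether repeat events count, which days form the denominator, or which exposure intervals are used. Those choices would be made after open-label data have been seen. The entry in SAP 9.0 also tells a reader of the study report that there is nothing to look for.

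**Working it through.** **1. Does another SAP section supply what is missing?**

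| Protocol commitment | Nearest SAP text | Substitute? |
|---|---|---|
| TEAE rate per 100 patient-years (11.9.3) | 8.5: "The exposure duration (days) will be calculated as the number of days exposed to study drug". 8.7.4, MADDERS: "Incidence per person-month will be summarized if applicable" | No. Exposure is derived but never linked to AEs. The one person-time measure is for abuse-related events and is conditional. |
| AE frequency and severity against exposure (11.9.3, synopsis) | 8.6.3: Kaplan-Meier time to discontinuation, separately for AE, lack of efficacy and any reason | Only for AEs that end treatment. |
| Time to stabilization of pain scores (11.10.2) | 8.6.2: time to a dose increase after Visit 10 | No. Different endpoint and different time origin. |
| COWS/SOWS items (11.9.7) | 8.7.2: totals, and COWS categories by dose level | No. |
| De Novo, Rollover, combined (11.9) | 7.1: finer subgroups, where necessary | Partly. They sum to the two cohorts, but no combined column is named. |

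There is no figure in the plan to reproduce. The arithmetic below only shows what a crude percentage can hide.

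**2. Patient-time compatible with the protocol's targets.** Protocol 11.2 gives about 600 dosed, at least 300 completing 26 weeks and at least 100 completing 52 weeks. Assume exactly 300 and 100. Patient-years = subject-weeks × 7/365.25.

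- Least: 100×52 + 200×26 + 300×0 = 10,400 weeks = 199.3 patient-years.
- Most: 100×52 + 200×52 + 300×26 = 23,400 weeks = 448.5 patient-years.
- If all 600 complete: 31,200 weeks = 597.9 patient-years.

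An assumed 60 subjects with one event each is 10% crude in every case. The rates are 30.1, 13.4 and 10.0 per 100 patient-years.

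**3. Same true rate, different retention.** Assume constant hazards and treat the 364 days as one year. With event rate *a* and dropout hazard *d* = −ln(one-year retention), crude incidence = a/(a+d) × (1 − exp(−(a+d))).

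For a = 0.60:

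- 40% retention: d = 0.9163, so 0.60/1.5163 × (1 − exp(−1.5163)) = 30.9%.
- 70% retention: d = 0.3567, so 0.60/0.9567 × (1 − exp(−0.9567)) = 38.6%. The gap is 7.7 points.
- 50% against 60% retention: 33.7% against 36.2%, a gap of 2.6 points before rounding.
- Equal retention: no gap.

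For a = 0.10 the corresponding gaps are 1.7 and 0.6 points.

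**4. Window mismatch.** TEAEs count to end of study, but SAP 8.5 exposure stops at the last dose. Mean on-drug time = 364 × (1 − retention)/d, which is 238 days at 40% retention and 306 at 70%. The 14 follow-up days are 14/238 = 5.9% and 14/306 = 4.6% of that. A rate that divides all TEAEs by on-drug days is overstated by those amounts if the event rate stays constant through follow-up.

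**5. Limits of a single overall rate.** Keep the total event hazard at 0.60 but put half of it (0.30) in the first 42 days and half in the remaining 322, with constant dropout. At 40% against 70% retention:

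- Crude incidence is 36.7% against 41.3%, a gap of 4.6 points.
- Expected events over mean on-drug time, counting repeats, are 0.470/0.655 and 0.541/0.841. After scaling by 365.25/364 this is about 72.0 against 64.5 per 100 patient-years.

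The hazards are identical, yet the rates now differ in the opposite direction. The rate therefore needs a breakdown by time interval.

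**The case against.** The strongest reply is that SAP silence does not cancel a protocol commitment. This SAP does not claim to supersede the protocol, and SAP 7.0 allows further analyses. The study is single-arm and descriptive, and no hypothesis test rests on these tables. All of that stands. A reader might infer that the sponsor has abandoned the analyses or can no longer do them; the documents do not support that. What is missing is their prespecified definition and an accurate SAP 9.0.

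On grouping, SAP 7.1 can govern the AE tables because SAP 8.7.1 names no grouping of its own, and treatment arm in SAP 8.7.5 may be template wording. This weakens the grouping point without removing it. SAP 7.1 is conditional and names no combined column, and SAP 8.7.6 states a different grouping outright.

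A reader might also infer that exposure-adjusted rates cure the problem, or that the crude tables will favour a particular cohort. Step 5 shows that a single rate can mislead when events come early. The documents give no retention by cohort, so no direction can be claimed.

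Finally, SAP 8.1 tabulates reasons for discontinuation by highest titrated dose. Everyone starts at the lowest dose and steps up, so early leavers can only fall in low-dose rows. It is tempting to call this a spurious dose trend of a given size. The plan offers no inputs for such a size, protocol 11.4 sets no grouping, and SAP 8.6.3 already analyses the timing of discontinuation. It is not a departure from the protocol.

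**Conclusion.** The point holds as a mismatch between protocol and SAP on the primary objective. Two AE analyses are promised without condition and are absent from SAP 8.7.1. Time to stabilization and the item-level withdrawal scores are also absent, two safety sections use a different grouping, and SAP 9.0 discloses none of it. These findings come from the text and need no assumption.

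The numerical size is illustrative only. With assumed rates of 10 to 60 per 100 patient-years and the assumed retention contrasts, the crude gap runs from nothing at equal retention to 7.7 points under constant hazards. It is smaller if events are early-loaded. The omission is recoverable and does not invalidate the study, but it should be put right before the data are analysed.

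**What to change.** 1. In SAP 8.7.1, add TEAE rates per 100 patient-years by preferred term, with a rule for repeat events and one window for both events and time. Either add the follow-up days to the patient-time, or report on-drug rates beside a separate table of events after the last dose. An on-drug rate alone would lose the withdrawal events, which SAP 8.7.1 recognises only after the last dose.
2. Add AE frequency and severity by interval since first dose in this study. Show Rollover Subjects separately by feeder-study treatment (NKTR-181 or placebo), because their earlier exposure differs.
3. Present SAP 8.7.1, 8.7.5 and 8.7.6 for De Novo, Rollover and all combined, with the SAP 7.1 subgroups as a finer split.
4. Define stabilization of pain scores, which protocol 11.10.2 does not do, and restore that analysis and the COWS/SOWS item summaries. Otherwise list their removal, and every other departure, in SAP 9.0.
5. Optionally, label the SAP 8.1 table by highest dose as descriptive and confounded with time on study, to be read with SAP 8.6.3.

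The cost is SAP wording, programming and additional tables. No new data are needed: the SAP already uses the exposure dates and AE start dates.
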